9.5 Secondary Surgical Interventions

All secondary surgical interventions will be recorded in the subject's medical records and CRFs and recorded as an adverse event and reported to the IRB according to local policies and to the FDA according the regulations found in 21 CFR 812.

9.6 Safety Monitoring

Subjects will be observed closely to detect any adverse events or complications that may have occurred. On the day of treatment and at each follow-up visit, subjects should be asked a non-leading question, such as "How are your eyes?" to determine whether any complications or adverse events might have occurred since the last visit. The presence or absence of adverse

events or complications will be documented. All exam findings, work-up, management, and sequelae relevant to an AE will be recorded on the AE CRF.

Ophthalmic safety will be evaluated by slit lamp biomicroscopy of the operated eye. In the case of an adverse event or complication, these tests, and any others deemed necessary, may be repeated before the next scheduled visit at the investigator's discretion. Appropriate supportive and/or definitive therapy may be administered as required. Any complications or adverse events will be recorded in the medical record/CRF.

9.7 Post-Study Procedures

Subjects will be discharged from the study after the second scheduled examination is complete.

9.8 Device Accountability

All use of the Slit Stent II will be under the direct supervision of the principal investigator or his/her designee. The investigational stents will be clearly labeled as investigational use only, and will have a clearly marked serial number. The receipt date and serial number will be recorded. The stents will be stored at the Kellogg Eye Center in a secure fashion, with access limited to the study team and their designee.

All records of receipt, use, and disposition of the devices will be maintained by the study team. At the completion of the study, there will be a final reconciliation by study personnel of devices shipped, implanted, and devices remaining. Any discrepancies noted will be investigated, resolved, and documented prior to return or destruction of unused devices. Stents destroyed on site will be documented in the study files.

9.9 Early Withdrawal from Study

Subjects will be advised that they are free to withdraw from the study at any time. The investigator may discontinue a subject if a serious adverse event occurs and it is in the subject's best interest not to continue in the study, or if the subject moves and the subject cannot complete the remainder of the follow-up visits. When a subject withdraws early from the study, a final examination will be performed at the time of withdrawal, if possible.

10.0 DATA ANALYSIS AND STATISTICAL CONSIDERATIONS

A detailed statistical analysis plan (SAP) will be developed for analysis of all data for this study. Required analyses and target endpoints that will be included in this SAP are summarized below. The methods by which each of these analyses is performed will be included in the SAP. The required analyses and target endpoints for the Slit Stent II include, but are not limited to, those listed below. If there are any discrepancies between the statistical analyses described in the SAP versus this protocol, the SAP will prevail. Tabulation of summary statistics, graphical presentations, and statistical analyses will be performed using SAS® and/or R software. All subjects who are enrolled in this study will be included in the safety analysis. All testing and confidence intervals will use a two-sided significance level of 5%.

Specific analyses for the six listed objectives are very similar to one another. Data will be summarized by treatment group (Slit Stent II or BIKA for DCR): counts and percentages for categorical variables, means and standard deviations for continuous variables. Additionally, 95% confidence intervals will be provided for each treatment group and for the difference between treatment groups. The confidence intervals for differences are keys to exhibiting the similarity between the Slit Stent II and the existing BIKA stent.

As this is a randomized experiment, control for pre-treatment variables is not necessary. However, a sensitivity analysis controlling for the baseline measurement of the outcome variable will be conducted. For example, post-surgery Lac-Q will be regressed on treatment and pre-surgery Lac-Q. If pre- and post-surgery measures are highly correlated, the confidence interval for the treatment effect will be narrower (more precise). If measurements are made at multiple post-surgery time-points, (generalized) linear mixed models will be used to estimate an overall (fixed) treatment effect while accounting for any correlation between measurements on the same person (random intercept).

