4.0 OBJECTIVES

- 1) Assess tolerance of patients to placement of Slit Stent II (Glasgow Benefits Index and Patient Stent Tolerance and Irritation Assessment)
- 2) Assess ocular surface irritation (objective and subjective) following stent placement (Glasgow Benefits Index and Patient Stent Tolerance and Irritation Assessment; Conjunctival and corneal epithelial surface exam and staining under the slit lamp)
- 3) Assess change in quality of life following surgery (Glasgow Benefits Index and Lac-Q Questionnaire)
- 4) Assess change in tearing/epiphora symptoms before and after surgery (Glasgow Benefits Index and Lac-Q Questionnaire)

- 5) Assess change in conjunctival tear lake measurement before and after surgery
- 6) Assess bacterial growth on stents after removal

All criteria will be summarized within the Slit Stent II treatment group. Formal comparisons will be made to no treatment effect and to the standard treatment (control group).

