7.1 Inclusion Criteria

Subjects in whom the subject and study eye meet all of the following criteria are candidates for this study:

1. 22 years of age or older.
2. Eligible for unilateral DCR surgery with stenting for treatment of epiphora secondary to nasolacrimal duct obstruction. Ability to instill post-operative eye drop
3. Signed written, informed consent.
4. Willingness and ability to comply with schedule for follow-up visits and postoperative evaluations.

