Appendix B: Lac-Q Questionnaire

The Lac-Q Questionnaire:

The Lac-Q questionnaire, published in 2011, is a patient symptom questionnaire developed for lacrimal drainage surgery.¹⁻² The questionnaire contains two scores, one is specific for eye-symptoms, and the other assesses the social impact of symptoms. (see below)

Lac-Q - The Lacrimal Symptom Questionnaire Name: _____ Number: _____ Date: _____

Social and lifestyle impact of tear duct problem

Which of these five statements is true about the tear duct problem overall in the last eight weeks?
 Please tick the box next to any true statement.

- Friends or family have commented about the watery eye problem.
- The watery eye problem has caused embarrassment in company.
- The watery / sticky eye problem has interfered with everyday activity, for example (underline each that applies):
 Reading .. Driving .. Wearing make-up
 Wearing glasses .. Hobbies
 Other activity (specify):
- The vision is sometimes blurred because of the watery / sticky eye problem.
- Medical attendance: visit to the family doctor's surgery, or the hospital eye clinic, because of tear duct problem.

(Scoring: score one point for each box ticked, maximum score =5)

Total score for social impact:

Problems with each eye separately

For each of the four problems (watery eye, pain, sticky eye or swelling), put a tick in the box next to the statement which best describes the situation over the last eight weeks.
 Use the left hand column for the left eye, and the right hand column for the right eye.

	Left	Right
• Watery eye		
No watery eye problem		
The eye waters occasionally, mainly outdoors		
Troublesome watering of the eye, indoors and outdoors, some days		
Troublesome watering of the eye most days		
Troublesome watering of the eye every day		
• Pain in or around the eye; soreness of eyelids		
No pain		
Some pain or soreness, but has not sought medical advice or treatment		
Pain or soreness, has used prescription eyedrops		
Painful and swollen (lacrimal abscess), requiring antibiotics or surgical drainage		

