• Sticky eye		
No problem with sticky eye		
The eye is sometimes sticky in the mornings		
The eye is sticky every day in the mornings		
The eye has sticky or mucous discharge throughout the day		
There is infected discharge leaking through the skin of the lower eyelid (fistula)		
• Swelling or lump at the medial canthus (mucocoele)		
No swelling or lump		
Swelling present, but only intermittently		
Swelling present all the time		

(Scoring: use numbers in central column) **Total scores for each eye:**

Lac-Q score (sum of three total scores):

Scores for the filled in questionnaire:

Social and lifestyle impact score (sum of social impact questions)

Left eye symptom score (sum of “left” column of symptom questions)

Right eye symptom score (sum of “right” column of symptom questions)

Lac-Q score (sum of all three total scores above)

LAC-Q QUESTIONNAIRE REFERENCES

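### Make the already planned baseline-adjusted comparison the main analysis for Lac-Q and tear lake height (a gain in precision only)

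*Combined protocol and SAP*

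**What the plan says.** Section 10.0 of the combined protocol and SAP reasons: "As this is a randomized experiment, control for pre-treatment variables is not necessary". It then adds that "a sensitivity analysis controlling for the baseline measurement of the outcome variable will be conducted" and gives the form of the model: "post-surgery Lac-Q will be regressed on treatment and pre-surgery Lac-Q". It accepts that the adjusted interval will be tighter when pre- and post-surgery values are highly correlated. For outcomes measured at several post-surgery visits it plans a mixed model with a random intercept and names no baseline covariate.

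The same section treats the confidence intervals for between-arm differences as central to showing that the Slit Stent II resembles the BIKA stent. Section 10.1 puts their margin of error at 0.57 SD with 25 per arm.

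Two roughly continuous outcomes have a baseline and are repeated at Day 5-14, Day 30-120 and Month 5-7: Lac-Q (Sections 9.1.3, 9.4, 10.5.3; Appendix D) and tear lake height (Sections 9.1.3, 9.4). Objective 5 in Section 4.0 is: "Assess change in conjunctival tear lake measurement before and after surgery".

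**The concern.** Randomization makes the unadjusted comparison unbiased, but it does not make it the most precise one available. In a trial that argues similarity from confidence intervals, with 25 per arm, width decides how much can be concluded. The plan recognises the gain from adjustment but leaves it out of the main result.

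A second point is left open. Objectives 3 to 5 speak of change, while Section 10.0 does not say whether the unadjusted comparison uses post-surgery values or change scores. Which of these is the more precise depends on a correlation that nobody knows yet, and the difference can be large.

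**Working it through.** **Inputs.** 25 per arm (Sections 7.0 and 10.1) and two-sided 5% (Section 10.0). The documents give no pre/post correlation ρ, so ρ is an assumed range. Half-widths are in SDs of the outcome, at one visit, with equal pre- and post-surgery SDs assumed.

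**The plan's own figure.** t(0.975, 48) × √(2/25) = 0.569 SD, which reproduces the stated 0.57.

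**Formulas.**
- Unadjusted change scores: 0.5687 × √(2(1 − ρ)).
- Baseline-adjusted: t(0.975, 47) × √[(2/25)(1 − ρ²)(1 + 1/46)]. The factor 1 + 1/46 is the expected cost of chance baseline imbalance, and 47 reflects the degree of freedom spent.

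| ρ (assumed) | Post values | Change scores | Adjusted | Adjusted against the better unadjusted option |
|---|---|---|---|---|
| 0 | 0.569 | 0.804 | 0.575 | +1.1% |
| 0.3 | 0.569 | 0.673 | 0.549 | −3.5% |
| 0.5 | 0.569 | 0.569 | 0.498 | −12.4% |
| 0.7 | 0.569 | 0.441 | 0.411 | −6.8% |

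**Break-even.** The ratio of squared half-widths at ρ = 0 is (0.5752/0.5687)² ≈ 1.023.
- Against post values: 1 − ρ² = 1/1.023, so ρ ≈ 0.15.
- Against change scores: 1.023(1 − ρ²) = 2(1 − ρ), so 1 + ρ = 2/1.023 and ρ ≈ 0.955 (equal SDs).

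**Fewer patients.** Section 9.4 expects some patients not to travel for the final visit. With an assumed 20 per arm, post values give 0.640. Adjusted half-widths are 0.650, 0.620, 0.563 and 0.464 at the same four correlations, and break-even is about 0.17.

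**Single trials.** The figures above are averages. In 20,000 simulated trials per correlation, the adjusted interval was narrower than the post-value interval in 20%, 40%, 76% and 98% of trials at ρ = 0, 0.15, 0.3 and 0.5. With integer scores floored at zero (20% zeros after surgery, assumed), the mean half-width was 0.566 unadjusted. Adjusted, it was 0.548, 0.502 and 0.423 at observed correlations of 0.29, 0.48 and 0.67.

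**Average over three visits.** With complete data the overall effect compares each person's three-visit mean. That mean has variance (1 + 2r)/3 for between-visit correlation r, and its squared correlation with baseline is 3ρ²/(1 + 2r). At ρ = 0.5 and r = 0.4 this is 0.25/0.6 = 0.417, so the width ratio is √(1 − 0.417) × √1.023 ≈ 0.77. Over assumed r of 0.4 to 0.6 the adjusted interval is about 5-7% narrower than the unadjusted post-value interval at ρ = 0.3 and about 18-23% narrower at ρ = 0.5. The cost at ρ = 0 is the same 1%.

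**What the documents suggest about ρ.** Appendix B asks: "Which of these five statements is true about the tear duct problem overall in the last eight weeks". The share of that 56-day window lying before surgery is (56 − 5)/56 = 91% at Day 5, (56 − 14)/56 = 75% at Day 14, (56 − 30)/56 = 46% at Day 30, and none from Day 56. The Lac-Q total also adds the symptom score of the other eye, although patients must be "Eligible for unilateral DCR surgery with stenting". Both features suggest a positive correlation that differs by visit. For tear lake height the documents give no such indication.

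**The case against.** The plan already commits to this regression, says when it will help, and will report both intervals. The unadjusted analysis is valid, so the point is only which result leads. That is fair, and it is why this is a suggestion and not an error.

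The correlation is unknown and could be low if surgery resolves symptoms in most patients. At 0.3 the average gain is 3.5%, and about a quarter of single trials would show a wider adjusted interval. This stands. Against it, the average loss at zero correlation is about 1%.

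The recall-window argument has limits. Screening may be up to 60 days before surgery, so a baseline Lac-Q at Day −60 covers Day −116 to −60, while the earliest post-operative window starts at Day −51, and the two need not overlap. The argument is also strongest at Day 5-14, when the score mostly describes the time before surgery. Both points stand. The first does not remove the expectation of some correlation, since both windows still describe the same patient's pre-surgical condition, and the other eye contributes at every visit.

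Finally, no stated decision rule changes. The only margin and power figure concerns the GBI, and neither Lac-Q nor tear lake height has a success criterion. That also stands. The intervals for these outcomes nevertheless belong to the similarity argument in Section 10.0.

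**Conclusion.** The point holds, as a matter of precision only. Baseline adjustment is confined to a sensitivity analysis for two outcomes that have a baseline. As the main analysis it would on average narrow the single-visit interval by 3.5% at an assumed correlation of 0.3 and 12.4% at 0.5, against the better unadjusted option. At 0.5 that is roughly the precision of 25/(1 − 0.25) ≈ 33 per arm without adjustment.

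From about 0.15 to 0.955 the adjusted interval is on average no wider than either unadjusted choice, so adopting it also settles the open question of post-surgery values or change. The plan's condition of a high correlation therefore understates when adjustment helps. These sizes rest on assumed correlations and equal pre- and post-surgery SDs. The case is better supported for Lac-Q than for tear lake height.

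**What to change.** In Section 10.0, or in the detailed SAP it announces:

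- Make the regression of the post-surgery value on treatment and baseline the main between-arm analysis for Lac-Q and tear lake height, and keep the unadjusted difference as the sensitivity analysis.
- State that the outcome is the post-surgery value.
- Where the mixed model over visits is used, add baseline and a baseline-by-visit term, because the Lac-Q correlation is unlikely to be equal across visits.
- Limit the change to these two outcomes. The GBI and the Patient Stent Tolerance and Irritation Assessment have no baseline, and the calculation here does not carry over to the ordinal Oxford staining grades.
- Reconcile Section 10.5.4, which sends slit lamp findings to line listings, with the between-arm comparisons that Sections 4.0 and 10.0 promise for every objective.

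The cost is SAP wording. No new data, visits or patients are needed. If the correlation is zero, the interval is on average about 1% wider (1.5% with 20 per arm).

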10.1 Sample Size

The recommended study size is 50 subjects: 25 in the treatment arm (Slit Stent II) and 25 in the control arm (BIKA for DCR). The sample size recommendation is based on two factors.

- It provides reasonable accuracy for estimates of proportions, means, and differences of proportions and of means. For categorical variables, the maximum half width of a 95% Wilson confidence interval for a single proportion is 0.18 (for $n=25$) and for a difference of two proportions is 0.27 ($n_1=n_2=25$). For continuous variables, the margin of error for a Welch t-interval for a mean is 0.41 standard deviations, and for a difference of two means it is 0.57 standard deviations. For example, if the standard deviation of the GBI score is 25 points, the margin of error for the confidence interval for the difference of treatment group GBI means is 14 points.
- It provides excellent power to show the new variation is non-inferior to the common lacrimal stent as measured by the GBI: Based on previous studies of lacrimal stents [11, 41-47] that assessed GBI, we estimate the standard deviation is about 25 points on the GBI scale and we set a non-inferiority boundary of $\delta = 20$ points ($20/25 = 0.80$, a 'large' effect in Cohen's taxonomy). If in fact the devices are equivalent (i.e., they have equal mean GBI scores, $\mu_{SSII} = \mu_{BIKA}$), then we have 87% power to demonstrate non-inferiority based on a single GBI measurement. Using all repeated observations would increase power even against a tighter non-inferiority boundary.

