10.5.2 Glasgow Benefit Inventory (GBI) Questionnaire

The effectiveness parameter evaluated will be the mean composite score for the GBI administered post-treatment at the 1-4 month post-operative follow-up visit. The GBI will be administered at each post-operative visit. It is believed that the positive effect of the surgery will have manifested itself in GBI score by the 2nd follow-up visit. A 95% t confidence interval will be used to estimate the mean score.

Scoring the GBI will follow the standard protocol (**Appendix A**). Positive scores indicate improvement from pre-treatment; negative scores indicate deterioration.

As part of the GBI protocol, it is expected that researchers may need to change the format or appearance of items to suit their purposes.

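### The 87% power for GBI non-inferiority is about 79% under the plan's own two-sided 5% rule, and the visit and model to be tested against the 20-point margin are not fixed

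*Combined protocol and SAP*

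**What the plan says.** **Margin and power.** Section 10.1 is the only place that gives the 20-point margin. It applies the margin to the difference in mean GBI between Slit Stent II and BIKA, with SD 25, 25 per arm and equal true means: "then we have 87% power to demonstrate non-inferiority based on a single GBI measurement". It does not name the visit. It then adds: "Using all repeated observations would increase power even against a tighter non-inferiority boundary".

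**Significance level.** Section 10.0: "All testing and confidence intervals will use a two-sided significance level of 5" per cent.

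**Visit.** Section 10.5.2: "The effectiveness parameter evaluated will be the mean composite score for the GBI administered post-treatment at the 1-4 month post-operative follow-up visit". The interval given there is for a mean, not an arm difference, and the margin is not mentioned: "A 95% t confidence interval will be used to estimate the mean score".

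**Repeated measurements.** Section 10.5.2 also says "The GBI will be administered at each post-operative visit". For outcomes measured at several post-surgery time-points, section 10.0 says "linear mixed models will be used to estimate an overall (fixed) treatment effect", with a random intercept. This sentence follows the description of a baseline-adjusted sensitivity analysis in the same paragraph. Section 10.0 separately promises 95% intervals for arm differences, without naming a visit or the margin.

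**Deferral.** Section 10.0: "A detailed statistical analysis plan (SAP) will be developed for analysis of all data for this study". That later SAP would prevail over the protocol. It is not part of the text supplied.

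**The concern.** There are two problems.

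First, the stated power and the stated significance level do not go together. A non-inferiority claim read from the lower limit of a two-sided 95% interval is a one-sided 2.5% test, and 87% is not the power of that test.

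Second, the plan points to two different GBI quantities that could be set against the 20 points: the difference at the 1-4 month visit, and one effect averaged over visits. By the schedule, stents come out at the day 30-120 visit, so a month 5-7 score is taken after removal in both arms. The Background says that an ordinary stent holds back full drainage until it is removed, which suggests a difference while the stents are in place. Averaging in a later visit would then understate a slit-stent advantage. The same averaging would shrink a temporary deficit. The documents do not predict such a deficit, but a non-inferiority test exists to detect one. If the deciding quantity is not named in advance, nothing in the supplied text prevents it being chosen after the results are known.

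**Working it through.** **Inputs.** From section 10.1: margin 20, SD 25, 25 per arm, true difference 0. From section 10.0: two-sided 5%. Assumed, because the plan gives no values: within-patient correlation 0.3, 0.5 or 0.7; equal variances; complete data unless stated otherwise.

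**Step 1: the plan's own figure.**
- Standard error of a single-visit difference: 25 × √(2/25) = 7.07.
- Noncentrality: 20 / 7.07 = 2.83, with 48 degrees of freedom.
- Noncentral t, one-sided 5%: power 87.4%. This reproduces the stated 87%.
- Noncentral t, one-sided 2.5% (lower limit of a two-sided 95% interval): power 79.1%. This does not.
- Reaching 87% at one-sided 2.5% takes 31 per arm (87.3%); 30 per arm gives 86.1%.

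**Step 2: what a pooled effect estimates.** With complete data, a random-intercept model with visit effects and one treatment term estimates the plain average of the visit-specific differences, whatever the correlation. The table takes the day 30-120 difference as 1.

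| Pattern (day 5-14, day 30-120, month 5-7) | Average | Share kept |
|---|---|---|
| 1, 1, 0 | 2/3 | two thirds |
| 0, 1, 0 | 1/3 | one third |
| 0, 1, 1 | 2/3 | two thirds |
| 1, 1, 1 | 3/3 | all |

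Section 9.4 expects some patients to miss the final visit. If 20% to 40% of final visits are missing (assumed), generalised least squares gives a share of 0.72 to 0.80 for (1, 1, 0) and 0.36 to 0.40 for (0, 1, 0). With only two GBI visits, (1, 1) keeps all and (0, 1) keeps half.

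**Step 3: precision gained by pooling.** Standard error over K visits = 25 × √[(2/25) × (1 + (K − 1)ρ)/K]. For K = 3 this is 5.16, 5.77 and 6.32 at ρ = 0.3, 0.5 and 0.7. At zero true difference and one-sided 2.5%, pooled power is 97%, 92% and 87%, against 79% for the single visit.

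**Step 4: stress cases.** These are not predicted by the documents. Take a true 20-point deficit at day 30-120. The day 30-120 test then declares non-inferiority 2.5% of the time. The pooled test over three visits does so as follows:

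| Deficit pattern | Pooled deficit | ρ = 0.3 / 0.5 / 0.7 |
|---|---|---|
| both stent-in visits, none later | 13.3 | 24% / 20% / 18% |
| day 30-120 only | 6.7 | 72% / 62% / 54% |
| equal at all three visits | 20 | 2.5% / 2.5% / 2.5% |

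**Step 5: how many visits would be pooled.** Section 9.4, Appendix D and the each-visit wording of section 10.5.2 give three GBI visits, and sections 5.0 and 8.1 support follow-up to about month 7. Section 9.0 gives the GBI at two post-operative visits, section 9.7 discharges patients after the second examination, and Table 10.2-1 stops at day 30-120. Section 8.2 lists a 5-7 month examination but also places all final procedures at the second visit.

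**The case against.** The best defence is that the plan can be read as a whole. Section 10.1 does attach the margin to an arm difference on one measurement, section 10.5.2 names the visit, and section 10.0 promises an interval for the arm difference. Together these lean towards day 30-120. The mixed-model sentence is conditional, sits beside a sensitivity analysis that uses Lac-Q as its example, mentions neither GBI nor the margin, and does not list the model's terms. Section 10.5.3 makes tolerance the primary goal, and the tolerance and irritation score is not collected after removal, so it is not affected. Interval precision is a separate justification for the sample size. All of this stands, and it keeps the second problem modest. It does not remove it: GBI meets the mixed-model condition, section 10.1 itself points to all repeated observations, and section 10.5 lists GBI among the primary effectiveness outcomes.

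A reader might infer more than the documents support:
- *That the margin is tied to no arm contrast at all.* Section 10.1 does tie it to one; the visit, model and decision rule are what is missing.
- *That the pooled effect is the planned primary test.* Its status is not stated.
- *That the trial would pass an inferior stent 18% to 72% of the time.* Those rates need the deficit patterns, the 20-point size and the correlations assumed in step 4.
- *That the gap will remain.* The later SAP may close it; this cannot be judged from the supplied text.

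None of these points bears on the power figure, which conflicts with section 10.0 whichever visit is used.

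**Conclusion.** The power statement is wrong as written. With the plan's own inputs and two-sided 5% rule, it is about 79%, not 87%. This rests on no outside assumption beyond reading non-inferiority from the lower limit of the two-sided 95% interval.

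The contrast point is real but smaller. The text leans towards the 1-4 month visit without saying that this difference, under a named model, is what is compared with 20 points. The pooled alternative answers the same question only if the arm difference is constant across visits. Otherwise, with three visits and complete data, it keeps between one third and two thirds of the day 30-120 difference in the patterns shown. If the difference is constant, pooling loses nothing and is more precise. The supplied documents do not establish which pattern will occur.

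**What to change.** 1. In section 10.1, restate the power as about 79% at two-sided 5% for 25 per arm.
2. In section 10.5.2 or the SAP, state that the deciding contrast is Slit Stent II minus BIKA in GBI at the day 30-120 visit, non-inferior if the lower limit of the two-sided 95% interval exceeds -20. Name the method: either the Welch interval already used in section 10.1, or a mixed model with categorical visit and treatment-by-visit terms.
3. Label the pooled effect and the other visits as supportive. Qualify the repeated-observations sentence in section 10.1: it adds power for the same question only under a constant effect.
4. Reconcile the number of GBI visits (sections 8.2, 9.0, 9.7 and Table 10.2-1 against sections 5.0, 8.1, 9.4, 10.5.2 and Appendix D), and say which visits enter any pooled effect.

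The cost is a few sentences, with no new data if the GBI is collected as in Appendix D. The downsides are a less favourable stated power and the loss of pooling's precision in the deciding test: about 79% power against about 92% at an assumed correlation of 0.5 with three visits.
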